#### 5.5 Interim Visits

Interim visits may occur at any time during the project and may be conducted at the clinic or at the affiliated community sites. Interim visits may occur for one or more of the following reasons: 1) Medical reasons (e.g., a client may want to discuss barriers to adherence not related to side effects; client may require an interim visit related to a priority health issues; client may require STD/HIV screening); 2) Reasons related to an adverse event for example, intolerable side effects; 3) Other reasons the participant may request. In general, participants requesting interim visits should contact their PN for triage. The PN will make a recommendation to the client on whether an interim visit is indicated or whether an alternate plan is warranted.

When interim visits in response to participant reports of AEs are completed, the physician, physician’s assistant or nurse practitioner member of the clinical team will clinically assess the reported event and provide appropriate medical care or make appropriate referrals. Participants with symptoms suggestive of acute HIV-infection syndrome will receive diagnostic testing to attempt to elucidate the cause of the syndrome, including HIV testing that includes testing for HIV RNA. Study medication will be stopped immediately if any HIV test is reactive or positive. All interim visits will be documented in the client’s clinical/study records. All interim clinical visits identified in the health information exchange from client’s primary or other health care provider (when applicable) will also be noted in the client’s clinical/study records and on applicable CRFs.

#### 5.6 Initiating or Starting PrEP after the Enrollment Visit

For any participant who has not taken PrEP or PEP in the past 60 days, PrEP may be restarted at Month 3 visit, after confirming PrEP eligibility according to the following Screening Visit parameters:

- HIV testing
- HBsAg testing
- Blood collection for creatinine test with calculation of creatinine clearance

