### 4.2 Study Product Regimen, Administration, and Duration

Once enrolled, all participants who agree to initiate FTC/TDF study product will be directed to take one FTC/TDF 200mg/300mg (Tenof-EM®) tablet orally once daily with or without food for up to 52 weeks.

The participant can decide to initiate FTC/TDF administration at any time after enrollment and week 48 of the study treatment period. Once initiated, the study participant may also decide to discontinue taking FTC/TDF study product at any time during the 52 week study treatment period. For participants who decide to initiate PrEP at or after Week 48, partnerships will be established as applicable with community partners in order to provide adequate clinical care and follow-up.

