#### **2. Informed consent**

Prior to screening, every potential participant demonstrating interest in study participation will have to sign the Informed Consent Form (See Appendix III). Consent procedure will be performed by a study staff member responsible for recruitment. In more details, the consent procedure is described in Section 8.

3. Randomization

Consenting participants will be randomized using the functionality in REDCap participant database using a pre-defined allocation schedule stratified by site.

4. Locator information

After signing the ICF, the participant will provide his contact information. Staff members will assure participants that the detailed follow-up information will be deleted if they are not enrolled in the study.

5. Behavioral and psychosocial survey

Structured interviews will be administered by an experienced interviewer using the questionnaire designed by study team (Appendix II). Baseline and follow-up questionnaires will not differ in content. Interview data will be directly entered into the online version of the participant questionnaire at the REDCap platform.

*Intervention provision (intervention staff)*

6. Assess participant's readiness for PrEP adherence

PNs will use a PrEP readiness tool to assess key predictors of PrEP adherence.

7. PrEP discussion

PrEP Education will be provided at each study visit to participants by PrEP Navigators with the option to start/continue, stop, or abstain from usage. A manual will be created for all sites to follow when discussing PrEP with participants based on safety and efficacy language found in the ICF under "Study Purpose".

8. Autonomy supportive adherence counseling

Adherence counseling will be provided to all participants who initiate PrEP at each study visit starting at the enrollment visit. The counseling makes use of self-determination theory that is designed to facilitate the client's integration of PrEP usage into his health behavioral routines and support the client in making his own decisions regarding adherence. Counseling will include the development of client-centered strategies to support the consistent daily adherence of PrEP. This counseling is delivered one-on-one by PrEP navigators during the study visits. The counseling will also include reminders not to share the medication and to contact project staff with questions about product use.

After each counseling session, the PN will fill out the Care Coordination Measurement Tool (CCMT).

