**APPENDIX I - SCHEDULE OF EVALUATIONS AND PROCEDURES**

	Pre-screening	Enrollment	Month 1, 3	Month 2,4,5 (by phone)	Month 6 (exit)	Interim visits
Administrative and Behavioral Evaluations/ Procedures						
Pre-screening	x					
Eligibility screening and demographic information		x				
Informed Consent, randomization		x				
Locator information		x	x	x		x
Behavioral and psychosocial survey		x	x		x	
Initial PrEP adherence readiness assessment (PN)		x				
Self-reported study product adherence assessment (PN)			x	x	x	x
Individual Interview for selected participants						x
Staff Focus Group (after all participants complete)						x
Intervention provision						
PrEP Discussion		x	x	x	x	x
Autonomy Supportive Adherence Counseling		x	x	x		x
PrEP Navigation and study product supply		x	x			x
SMS reminder customization 		x	x	x		x
SMS reminder 		x	xx	xx		
HIV/ STI behavioral risk-reduction counseling		x	x		x	x
Provision of prevention supplies		x	x		x	x
Clinical Evaluations/ Procedures						
Medical history including medications		x				
Symptom-Driven Physical Examination		x				
Laboratory Evaluations/Procedures						
HIV screening testing		x	x 		x	
HBsAg testing		x			x	
Renal function tests (creatinine)		x				
Calculated creatinine clearance		x				
DBS storage for possible Pharmacology testing		x	x		x	

 Experimental arm only.

 Month 3 only

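### Participant-chosen starts or restarts of PrEP outside Month 3 have no stated testing condition, and at Month 3 the visit schedule lists one of the three tests that section 5.6 requires

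*Protocol*

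**What the plan says.** Section 5.6 is headed as covering PrEP begun after the Enrollment visit, but its text deals only with a restart at Month 3: "For any participant who has not taken PrEP or PEP in the past 60 days, PrEP may be restarted at Month 3 visit". The same sentence makes this restart conditional on re-testing and names three parameters: HIV, HBsAg, and creatinine with calculated clearance.

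Other places leave wider routes to drug:

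- 4.2: "The participant can decide to initiate FTC/TDF administration at any time after enrollment and week 48 of the study treatment period".
- 5.2 item 7: "PrEP Education will be provided at each study visit to participants by PrEP Navigators with the option to start/continue, stop, or abstain from usage".
- 5.3 supplies two months of drug at Month 1 and three months at Month 3.
- Appendix I marks the row "PrEP Navigation and study product supply" at Enrollment, Months 1 and 3, and interim visits.

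Appendix I marks the laboratory rows as follows:

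- "HIV screening testing": Enrollment, Month 3 (a footnote excludes Month 1) and Month 6.
- "HBsAg testing": Enrollment and Month 6.
- The creatinine and clearance rows: Enrollment only.

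The 5.3 procedure list agrees with Appendix I on HIV at Months 3 and 6, and names neither HBsAg nor creatinine. Section 7.1, under incident seroconversions, places HIV testing at all study visits.

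**The concern.** The protocol treats all three results as reasons to withhold drug. A reactive HIV test ends dosing at once (5.5), a positive HBsAg excludes the participant (5.2 item 16), and an elevated creatinine leads to an instruction to stop (5.2 item 17). Section 5.6 applies the same logic to someone returning after 60 days off drug, but only at Month 3.

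A participant who first accepts PrEP at Month 1, or who starts or returns at an interim visit, falls outside the wording of 5.6, while other sections appear to allow supply. At Month 3, staff working from the 5.3 list or the Appendix I grid see nothing to prompt two of the three tests. Drug could then go to someone who has acquired HIV or hepatitis B, or whose renal function has changed, since the last test.

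These events are foreseen. Section 7.1 defines discontinuation as 30 or more consecutive days of missed doses, and 7.3.1 plans Kaplan-Meier plots of the time until discontinuers restart.

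**Working it through.** No sample-size or power figure is involved. The check sets the provisions side by side and counts.

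**1. Month 3 restart.** Tests required by 5.6: 3 (HIV, HBsAg, creatinine/clearance). Listed at Month 3 in 5.3: 1 (HIV). Marked at Month 3 in Appendix I: 1 (HIV). Missing from both: 3 − 1 = 2. Neither place carries an entry for participants who are restarting, although the HIV row already has a footnote, so the format allows one.

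**2. Routes to drug after Enrollment, and the test each one states.**

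| Route | Source | Stated test |
|---|---|---|
| Restart at Month 3 after 60 days off | 5.6 | HIV, HBsAg, creatinine/clearance |
| Initiation at any time after enrollment | 4.2 | none |
| Option to start at each visit | 5.2 item 7 | none |
| Supply at Month 1 | 5.3 | none |
| Supply at interim visits | Appendix I | none (0 of 3 marked) |
| Re-challenge after raised creatinine | 6.6.2 | creatinine below 1.3-fold above baseline |
| Restart after low clearance | 6.6.3 | re-test of at least 60 mL/min |
| Resumption after an exclusionary medication | 6.7 | creatinine within 1.3-fold above baseline, and negative HIV test |

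The gap therefore lies in the elective routes. The three clinician-hold routes have laboratory conditions, though none asks for HBsAg and none governs a participant who simply starts late or returns after stopping.

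**3. Age of the last scheduled test when drug is supplied.** Assume Enrollment is day 0, Month 1 day 30, Month 3 day 90 and Month 6 day 180. Scheduled HIV tests then fall on days 0, 90 and 180, HBsAg on days 0 and 180, and creatinine on day 0.

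- First start at Month 1: all three results are 30 − 0 = 30 days old.
- Restart at Month 3 run from the visit list: HIV is current; HBsAg and creatinine are 90 − 0 = 90 days old.
- Extreme case, interim supply on day 179: HIV is 179 − 90 = 89 days old; HBsAg and creatinine are 179 − 0 = 179 days old.

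The 89 days lie within the three-month monitoring interval mentioned in 1.1. The longer gap concerns HBsAg and creatinine.

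**4. HIV testing in 7.1.** Scheduled follow-up contacts: Months 1 to 6, so 6, of which Months 2, 4 and 5 are by telephone. In-person follow-up visits: 6 − 3 = 3 (Months 1, 3, 6). Those with a scheduled HIV test: 2 (Months 3 and 6). The 7.1 statement fails even if it is limited to in-person visits, because Month 1 has no test.

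**The case against.** The strongest reply is that 5.6 is the dedicated section and should control. Read literally, it authorises no restart outside Month 3. Item 7 of 5.2 describes the content of education. The sentence in 4.2 carries week-48 text that does not fit a 6-month trial, so it is weak evidence of an intended route. The interim mark sits on a combined navigation-and-supply row and may mean only resupply to a current user. Section 5.5 also lists STD/HIV screening among the reasons for an interim visit. Section 5.0 calls Appendix I an overview, binds providers to Ministry of Health initiation requirements and refers to SOPs.

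Much of this stands, and it limits the point in four ways.

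- A reader might infer that no restart route outside Month 3 has a testing condition. Sections 6.6.2, 6.6.3 and 6.7 show otherwise.
- A reader might infer that the schedule flatly contradicts 5.6 at Month 3, or that sites would certainly skip the tests. The 5.6 tests apply to a subset, so their absence from the routine grid is an unmarked conditional. Ministry rules or SOPs, whose content is not given, may partly cover it.
- The day-179 case is extreme, and its creatinine gap is not specific to late starters: nobody has a scheduled creatinine after Enrollment.
- A reader might infer that 5.6 settles that the creatinine result must be in hand. Its wording about confirming eligibility points that way, but it lists blood collection, and 5.2 item 17 deliberately dispenses at Enrollment before the result.

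The reply does not close the gap. If 5.6 controls, 4.2 and 5.2 item 7 need correcting. If it does not, the elective routes need a test. HIV screening as a possible reason for an interim visit is not a condition on supplying drug there. External rules cannot align 5.6 with the protocol's own schedule.

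**Conclusion.** The point holds for elective starts and restarts. Outside Month 3 they have no stated testing condition, although four provisions leave them open. At Month 3, the visit list and Appendix I show 1 of the 3 tests that 5.6 requires. Section 7.1 misstates the HIV testing schedule.

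This should be corrected because it concerns a safety check before drug is given: a late first start at Month 1 or at an interim visit could be supplied without a current HIV test. It is a correction of wording and schedule. The documents do not support reading it as a threat to the primary adherence comparison, and none is claimed. The protocol gives no rate of late starts or restarts, so the number affected is unknown. The test ages above rest on 30-day months and on visits held exactly on schedule. Confidence is moderate, because local requirements and SOPs that are not shown may already cover part of the gap.

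**What to change.** 1. **Section 5.6.** Extend the rule to any elective first start after Enrollment, and to any restart after 60 days off drug, at any dispensing visit including interim visits. Require HIV and HBsAg results before dispensing, and creatinine drawn at that visit. State whether the creatinine result is awaited (about 3 days, per 5.2 item 17) or handled by dispensing and recalling, as at Enrollment. At Month 1 this can concern only a late first start, because 60 days off study drug cannot yet have passed.
2. **Appendix I and 5.3.** Add a footnote, *if starting or restarting, see 5.6*, to the HIV, HBsAg and creatinine/clearance rows for the Month 1/3 and interim columns, and put the same line in the 5.3 list.
3. **Section 7.1.** State HIV testing as Enrollment, Months 3 and 6, and whenever 5.5, 5.6 or 6.7 requires it.

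The cost is a reworded rule, a footnote, one added line and one corrected sentence. In operation it is up to three tests already in use per late start or restart, plus the wait for creatinine if the team chooses it. Such visits must be held at the clinical site, whereas 5.5 also allows interim visits at community sites. The change does not reach a participant who stops and later resumes from tablets at home, since no dispensing visit occurs; counseling would have to cover that case.

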## **5.7 Premature Study Discontinuation**

Participants may voluntarily withdraw from the study for any reason at any time. Site Coordinators may, with the approval of the PI withdraw participants before their scheduled termination visit to protect their safety, and/or if participants are unable or unwilling to comply with study procedures. Participants also may be withdrawn if the study sponsors, government or regulatory authorities, or site IRBs terminate the study prior to its planned end date. Study staff will record the reason(s) for all withdrawals in participants' study records. The Month 6 visit schedule should be followed when possible, in the event that a participant chooses to withdraw from the study. If a participant chooses to withdraw, data collected from this participant will be deleted and will not be used for analysis. In all other cases, participant information will be used for analysis.

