### 3.4 Participant Retention

Once a participant enrolls in this study, the study sites will make every effort to retain him/her for 6 months of follow-up to minimize possible bias associated with loss-to-follow-up. The study team recognizes that PWID represent a heterogeneous population requiring multiple methods to meet their needs, and also recognizes the importance of interacting with the participants in a culturally competent manner. A basic philosophy of the retention strategy is that follow-up begins at recruitment and is a priority at every visit. Components of such procedures include:

- Thorough explanation of the study visit schedule and procedural requirements during the informed consent process, with re-emphasis at each study visit.
- Thorough explanation of the importance of both study arms (intervention and standard of care) to the overall success of the study.
- Collection of detailed locator information at the Screening visit, with active review and updating of this information at each subsequent visit.
- Use of appropriate and timely visit reminder mechanisms.
- Visit calendars, flyers or other handouts will be offered at enrollment to assist with retention.
- Mobilization of trained outreach workers or “tracers” to complete in-person contact with participants at their homes and/or other community locations.
- Regular communication with the study community at large to build trust and increase awareness about substance use treatment and HIV/AIDS.

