### 3.5 Participant Withdrawal

Regardless of the participant retention methods just described, participants may voluntarily withdraw from the study for any reason at any time. The Investigator also may withdraw participants from the study in order to protect their safety and/or if they are unwilling or unable to comply with required study procedures after consultation with the Principal Investigator and study clinician. Study staff will record the reason(s) for all withdrawals from the study in participants’ study records.

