## 6.2 Adverse Event (AE) Reporting

Adverse events (AE) are defined as any untoward medical occurrence experienced by participants during the study, and may or may not have a causal relationship with the treatment. Information regarding all AEs regardless of seriousness or severity will be recorded in the participant's source files. Grade 3 and higher adverse events and all creatinine AEs will be recorded on study CRFs. All SAEs must be reported on AE Log CRF. All AEs that result in a clinical hold or permanent discontinuation of study product are reported on AE Log CRF regardless of grade. Grade 3 and higher clinical AEs will be referred to a study clinician at the time of the visit.

All critical laboratory values will be reported as applicable per site SOPs. Participants who are not present at the study site at the time a laboratory AE requiring retesting or follow-up is identified will be followed as deemed clinically appropriate. With appropriate permission of the participant, and whenever possible, records from non-study medical providers related to untoward medical occurrences will be requested and required data elements will be recorded on study CRFs and/or in the participant's medical chart. All AEs regardless of severity will be followed clinically, until the AE resolves or stabilizes as per the appropriate toxicity algorithm. AEs will be assessed for all participants, regardless if they continue PrEP or not, after enrollment through the final study visit.

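### Section 5.7 deletes all data of participants who choose to withdraw: a post-randomisation exclusion that can bias the arm comparison and removes their adverse events from the final tables

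*Protocol*

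**What the plan says.** Section 5.7 sets two data rules by type of exit. For a participant's own decision to leave: "If a participant chooses to withdraw, data collected from this participant will be deleted and will not be used for analysis". For everything else: "In all other cases, participant information will be used for analysis". The deletion rule makes no exception for data collected before withdrawal, for any endpoint, or for safety data.

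The same section says "Participants may voluntarily withdraw from the study for any reason at any time", asks that "The Month 6 visit schedule should be followed when possible, in the event that a participant chooses to withdraw from the study", and adds "Study staff will record the reason(s) for all withdrawals in participants' study records". Section 3.5 repeats the instruction to record reasons.

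Other sections bear on the rule:
- Section 6.2: "AEs will be assessed for all participants, regardless if they continue PrEP or not, after enrollment through the final study visit". It also sends every serious event to the AE log form.
- Section 7.3.2 plans a tabulation of adverse events, in total and by grade.
- Section 2.1 makes the between-arm comparison of adherence and retention on PrEP the primary objective (the Schema says persistence).
- Section 7.3.1 analyses high adherence at months 3 and 6 by GEE, and time to first discontinuation by Kaplan-Meier.
- Section 3.4 asks sites to retain participants "to minimize possible bias associated with loss-to-follow-up".

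**The concern.** Randomisation is done at the Enrollment visit (Section 5.2, Appendix I), and a participant may withdraw at any later time. Section 7.1 describes the trial as open-label, so the decision can depend on the arm. Deleting those who choose to leave therefore defines the analysed groups by something that happens after allocation, and the comparison is no longer between the groups as randomised.

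Three things are at stake.
- **Adherence.** A withdrawer contributes nothing to the GEE, even if a month 3 sample had been taken.
- **Persistence.** The follow-up time and any discontinuation already observed are removed. Censoring at withdrawal would have kept both.
- **Safety tables.** Adverse events are collected data, so the literal rule takes withdrawers out of the final tabulation.

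The rule is also uneven. A participant who stops attending, or whom staff withdraw for not complying, is analysed. One who announces the decision is erased. Similar behaviour is treated in opposite ways according to how an unblinded site records the exit.

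No analysis plan can repair this, because the data would no longer exist.

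**Working it through.** **Step 1. The passages side by side.**
- Section 5.7 asks for the Month 6 procedures at withdrawal, then deletes what they produce.
- Section 6.2 assesses adverse events in all participants, and Section 7.3.2 tabulates them. Section 5.7 removes one group of these participants from that table.
- Section 9.1 has the blood spots assayed in batches at study end. At withdrawal there are usually stored specimens and no results yet, so a replacement rule has to name specimens as well as data.

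**Step 2. Inputs for the size.** The plan gives no figure to reproduce.
- 200 participants randomised 1:1, so 100 per arm (Schema).
- Planning adherence rates of 33%, 50% and 67% (table in Section 7.2).
- Voluntary withdrawal by arm: not given. The values below are assumptions. The 10% to 20% loss to follow-up in Section 7.2 is not this quantity, since those lost are kept in the analysis.
- Adherence among withdrawers, q: not given, so shown as a range.

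**Step 3. Formula.** Let p be true adherence in both arms (no effect) and w the share withdrawing. After deletion the reported rate is (p − wq)/(1 − w). The false difference between arms is (p − q) × [w₂/(1 − w₂) − w₁/(1 − w₁)].

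For w₁ = 5% and w₂ = 15% the bracket is 0.15/0.85 − 0.05/0.95 = 0.1765 − 0.0526 = 0.1238. With p = 40% (assumed):

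| q | Arm with 5% withdrawal | Arm with 15% withdrawal | False difference |
|---|---|---|---|
| 0% | 0.40/0.95 = 42.1% | 0.40/0.85 = 47.1% | +5.0 points |
| 20% | 0.39/0.95 = 41.1% | 0.37/0.85 = 43.5% | +2.5 points |
| 40% | 40.0% | 40.0% | 0 |
| 60% | 0.37/0.95 = 38.9% | 0.31/0.85 = 36.5% | −2.5 points |

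Differences are taken before rounding (0.1238 × 0.20 = 0.0248 for the second and fourth rows). With 5% versus 10% withdrawal and q = 0, the rates are 42.1% and 0.40/0.90 = 44.4%, a difference of 2.3 points.

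**Step 4. At the plan's own adherence rates**, with 5% versus 15% withdrawal and q = 0. The rejection rate is for a pooled two-proportion z-test at an assumed two-sided 5%, with 95 and 85 left in the arms. It is a single-time-point stand-in for the GEE.

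| p | Reported rates | False difference | Rejection rate with no effect |
|---|---|---|---|
| 33% | 34.7% vs 38.8% | +4.1 points | 8.8% |
| 50% | 52.6% vs 58.8% | +6.2 points | 13.2% |
| 67% | 70.5% vs 78.8% | +8.3 points | 24.5% |

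If withdrawers have half the average adherence, the differences are 2.0, 3.1 and 4.1 points. If 10% withdraw in both arms there is no false difference, but with q = 0 a true 50% is reported as 0.50/0.90 = 55.6% in each.

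**Step 5. What retention alone does not recover.** Someone who leaves before month 3 without an exit sample has no value at month 3 or 6 under either rule. If that held for every withdrawer, an observed-case analysis with q = 0 would still show 42.1% versus 47.1%. Counting missing as not adherent restores 40% versus 40% when q = 0, but gives 39% versus 37% when q = 20%. It is therefore a sensitivity analysis and does not settle the answer.

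**The case against.** The strongest reply is that the rule is narrow. It applies only to a participant's own choice to leave. Loss to follow-up, incarceration and withdrawal by the investigator are all analysed, and nothing in the protocol suggests that voluntary withdrawal will be common or unequal. This stands, and it is why the figures above are only illustrations.

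A reader might infer four stronger things that the protocol does not support.
- **That withdrawal is tied to stopping PrEP, side effects or dislike of the messages.** Sections 4.2 and 5.2 let a participant stop PrEP and stay in the study, Section 5.4 lets message settings be changed, and Section 7.1 treats discontinuation as an analysed event. A link is plausible but not stated.
- **That the arm losing more people always looks better.** The table in Step 3 shows no difference, or a reversed one, when withdrawers adhere as well as or better than the rest.
- **That safety oversight is lost.** Section 6.4 sends serious events to the principal investigator within three reporting days, and Section 6.1 has safety reports reviewed about monthly. Events can be seen before deletion, and reports already made may survive elsewhere. What is threatened is the final tabulation.
- **That keeping the data removes the whole false difference.** Step 5 shows that it does not.

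Deletion may also be a promise made to participants. Section 8.1 lets them withdraw consent, and Section 8.3 acknowledges possible access by law enforcement. The consent forms are not available here. That is a reason to allow erasure on request. It does not justify making erasure automatic for everyone who stops taking part.

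**Conclusion.** The point holds and needs correcting before data are deleted. Section 5.7 writes a post-randomisation exclusion into an open-label comparison. It conflicts with the all-participant safety assessment in Section 6.2, the tabulation in Section 7.3.2 and its own request for an exit visit. Those conflicts, and the loss of samples and discontinuations already collected, depend on no assumption about rates.

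Bias in the arm comparison is conditional: withdrawal must differ by arm and be related to adherence. With 40% true adherence and 5% versus 15% withdrawal, the false difference runs from +5.0 to −2.5 points as withdrawers' adherence goes from 0% to 60%. With 5% versus 10% and non-adherent withdrawers it is about 2 points. All withdrawal shares are assumed.

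**What to change.** Replace the deletion sentence in Section 5.7 with text to this effect:

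> Data and specimens collected up to and including the withdrawal visit (Month 6 schedule), where the participant agrees to that visit, are retained and analysed in the randomised arm. No data are collected after that. In the persistence analysis, observed PrEP discontinuations count as events and other withdrawers are censored at withdrawal. All adverse events and serious adverse events up to withdrawal stay in the safety tables. Data are erased only on an explicit separate request, and the number of such requests is reported by arm.

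Add a sensitivity analysis for adherence outcomes missing after withdrawal, for example counting missing as not adherent.

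The cost is one protocol sentence, consent wording to match, and approval of the change by the institutional review board. It needs no extra participants and no visits beyond the exit visit that Section 5.7 already requests.
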